### 12.1 Analysis sets

The Enrolled Set (ENS) includes all patients who signed an ICF and are assigned patient numbers.

The Full Analysis Set (FAS) comprises all patients to whom study treatment has been assigned and who received at least one IVT injection of study treatment.

The Safety Set includes all patients who received at least one IVT injection of study treatment.

The Per-Protocol Set (PPS) is a subset of patients of the FAS without PDs with impact. The list of PD criteria will be provided in a separate document.

However, when assessing the robustness of the overall efficacy conclusions, considerations will be given to the analysis based on the estimand using FAS and PPS. Expectation of comparing of both estimands is to have similar conclusions. Inconsistencies in the results will be examined and discussed in the Clinical Study Report (CSR).

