### **12.4.3 Handling of missing values/censoring/discontinuations**

For patients who:

- Discontinue study treatment but continue in the study, the efficacy data will be censored at the time the patient stopped study treatment in the study eye.
- Interrupt treatment, the efficacy data will be censored at the time the study treatment was first interrupted.

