2.2 Analysis sets

Enrolled Analysis Set (ENR): The ENR set includes all patients who signed an ICF and are assigned patient numbers.

Full Analysis Set (FAS): The FAS comprises all patients to whom study treatment has been assigned and who received at least one IVT injection of study treatment.

Safety Set (SAF): The SAF set includes all patients who received at least one IVT injection of study treatment.

Per-Protocol Set (PPS): The PPS is a subset of patients in the FAS without PDs with impact. The list of PD criteria will be provided in edit checks specification (ECS) document.

Full Analysis Set Estimand (FAS-EST): The FAS-EST comprises all patients who are in the FAS and did not discontinue treatment in the entire study due to COVID-19.

Per-Protocol Set Estimand (PPS-EST): The PPS-EST is a subset of patients of the FAS-EST without PDs with impact.

When assessing the robustness of the overall efficacy conclusions, considerations will be given to the analysis based on the estimand using FAS-EST and PPS-EST. The expectation for comparing both estimands is to have similar conclusions. Inconsistencies in the results will be examined and discussed in the CSR.

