2.5 Analysis of the primary objective

2.5.1 Primary endpoint

OCT-A will be used in this study to assess the morphological response of patients to brolucizumab. In terms of percentage change in CNV lesion area (at the biggest surface) (mm²).

The primary endpoint is the percentage change in CNV lesion area measured by OCT-A from Baseline to Week 12 in the study eye. The percentage change from Baseline at Week 12 in the lesion area will be derived as follows:

([Lesion area at Week 12 – Lesion area at Baseline]*100)/ Lesion area at Baseline

Descriptive statistics (n, mean, std, median, min and max) for the primary endpoint (actual value, change from Baseline, percentage change from Baseline) will be presented based on observed data using the FAS. Furthermore, a 2-sided 95% CI using Student's t-distribution will also be provided. In case of significant outliers or deviations from normality assumptions then IQR will be presented.

The last observation carried forward (LOCF) method will be used as sensitivity analysis to impute missing record for CNV lesion area at post baseline. If there is significant amount of missing record then another table with LOCF records should be created.

The above analysis will be done only on the study eye. The analysis will be performed on FAS. The analysis will be performed on the PPS, if there is more than a 10% difference in patients, between the FAS and PPS.

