TRT04	Short treatment window between treatment	Included in everything	0
TRT05	Treatment > 3 days after injection visit	Included in everything	0
TRT06	Injection given at Week 12	Excluded from PPS	2
TRT07	Q8W IVT out of window	Included in everything	0
TRT08	Q12W IVT out of window	Included in everything	0
TRT09	COVID-19 Drug supply change	Included in everything	0

Deviation ID	Description of Deviation	Exclusion in Analyses	Severity code
TRT10	COVID-19 Treatment not given	Included in everything	0
TRT11	Missed Injection loading phase	Excluded from PPS	1
TRT12	Missed Injection	Included in everything	0
TRT13	No Disease activity but injection is given	Included in everything	0
TRT14	Treatment admin prior effic/safty evaluation	Included in everything	0
TRT15	Treatment given at EOS	Included in everything	0
WITH01	Withdrew consent not discontinued	Excluded from FAS and PPS	1
OTHER01	Patient rescreened > once	Included in everything	0
OTHER02	Severe ICH-GCP non-compliance	Excluded from FAS and PPS	1
OTHER03	New ICF is missing-rescreened	Excluded from FAS and PPS	1
OTHER04	Mishandling IP	Included in everything	0
OTHER05	Temperature excursion IP administered	Included in everything	0
OTHER06	Treatment regimen wrongly adjusted	Included in everything	0
OTHER07	Missed mandatory visit	Excluded from PPS	2
OTHER08	Missed injection visit	Included in everything	0
OTHER09	FA out of window	Included in everything	0
OTHER10	Rescreen due to BCVA results	Included in everything	0
OTHER11	Rescreen >14days w/o screening procedure	Included in everything	0
			1
OTHER13	COVID-19 Missed visit	Included in everything	0
OTHER14	COVID-19 Visit not at site	Included in everything	0
OTHER15	COVID-19 Assessment changed	Included in everything	0
OTHER16	COVID-19 Discontinuation Included in everything		0
OTHER17	Efficacy assessment not done Excluded from PPS		2
OTHER18	Safety assessment not done Included in everything		0
OTHER19	BCVA not done correctly Included in everything		0
OTHER20	Visit window > 7 days Included in everything		0
OTHER21	Vital signs/safety call not done Included in everything		0
OTHER22	Imaging analyzed after WoC Included in everything		0

Table 5-2 Patient Classification

Analysis Set	Severity codes that cause a subject to be excluded
ENR	NA
FAS	1
FAS-EST	1
PPS	1,2 (All specified PD in Table 5.1 due to COVID)
PPS-EST	1, 2 (All specified PD in Table 5.1 due to COVID-19)
SAF	NA

6 Reference

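### A missed loading-phase injection (TRT11) is a PPS-only exclusion by its text but a FAS exclusion by its severity code, so membership of the primary analysis set has two answers

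*SAP*

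**What the plan says.** Protocol Section 12.1 states that the FAS "comprises all patients to whom study treatment has been assigned and who received at least one IVT injection of study treatment". SAP Section 2.2 repeats this: "The FAS comprises all patients to whom study treatment has been assigned and who received at least one IVT injection of study treatment". Protocol Section 12.4.2 and SAP Section 2.5.1 both place the primary analysis on observed data in the FAS.

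SAP Section 5.5 then turns protocol deviations into set membership in two steps. Table 5-1 gives each deviation a text entry naming the sets it affects, and a severity code. Table 5-2 has a column headed "Severity codes that cause a subject to be excluded": code 1 for the FAS and FAS-EST, codes 1 and 2 for the PPS and PPS-EST, none for the Safety Set.

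For TRT11, "Missed Injection loading phase", the text entry names the PPS alone and the code is 1. The row is the same in SAP Amendment 2.0 and in SAP Addendum 1.0.

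Two other rules bear on the consequences. SAP Section 2.5.1 makes the PPS analysis conditional: "The analysis will be performed on the PPS, if there is more than a 10% difference in patients, between the FAS and PPS". Protocol Section 12.4.3 says that for patients who interrupt treatment, "the efficacy data will be censored at the time the study treatment was first interrupted".

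A related entry is OTHER16, "COVID-19 Discontinuation", which Table 5-1 gives code 0 and keeps in all sets. SAP Section 2.2 says: "The FAS-EST comprises all patients who are in the FAS and did not discontinue treatment in the entire study due to COVID-19".

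**The concern.** A programmer who builds the sets from the text column keeps a patient with a missed loading injection in the FAS. One who builds them from the codes, as Table 5-2 directs, removes that patient. The two routes give different primary analysis sets, and no passage ranks them.

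The code route drops treated patients from the FAS because of something that happened after baseline, which the FAS definition does not provide for. It also moves the FAS towards patients who received all three loading injections, the exposure whose effect the Week 12 endpoint measures. The primary mean and CI, the LOCF sensitivity table and the secondary efficacy summaries all inherit the choice. Because the PPS is the same under both routes, the code route also narrows the FAS–PPS gap and makes the conditional PPS analysis less likely to run.

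**Working it through.** **Row check of Table 5-1 against Table 5-2 (SAP Addendum 1.0)**

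| Rows | Text removes from | Code | Code removes from | Agree? |
|---|---|---|---|---|
| INCL01, INCL03, INCL04, WITH01, OTHER02, OTHER03 | FAS and PPS | 1 | FAS and PPS | Yes |
| INCL05, EXCL01, EXCL12, EXCL18, EXCL27, TRT01, TRT02, TRT06, OTHER07, OTHER17 | PPS | 2 | PPS | Yes |
| TRT11 | PPS | 1 | FAS and PPS | **No** |

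TRT11 is the only legible exclusion row whose text and code disagree. One further code 1 between OTHER11 and OTHER13 has no readable ID or text and was not counted.

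**The plan's own precision figure**

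Inputs from Protocol Section 12.8.1 and SAP Section 3: SD 35, two-sided 95% CI, half-width 5.0, 10% loss.

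- Normal approximation: n = (1.96 × 35 / 5)² = 188.2, rounded up to 189.
- Inflation: 189 / 0.90 = 210.
- With Student's t, half-width at n = 189 is t(0.975, 188) × 35 / √189 = 5.02, which prints as 5.0.

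The stated 189 and 210 reproduce.

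**Effect on precision if TRT11 patients leave the FAS** (shares of the 189 evaluable are assumed)

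| Share removed | n left | Half-width |
|---|---|---|
| 0% | 189 | 5.02 |
| 2% | 185 | 5.08 |
| 5% | 180 | 5.15 |
| 10% | 170 | 5.30 |
| 15% | 161 | 5.45 |

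**Effect on the mean**

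If a share p of evaluable patients has TRT11 and their mean percentage change differs by D points from that of the rest, removing them moves the FAS mean by p × D. With assumed values, this runs from 0.05 × 10 = 0.5 points to 0.10 × 30 = 3.0 points. The documents give neither p nor D, nor the sign of D.

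**Effect on the PPS trigger**

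Take 210 treated patients, and read the 10% as a share of the FAS (the SAP does not name the denominator). Let a be the number with TRT11 and no other code-1 deviation, and b the number removed from the PPS by code 2 alone. Assume no other code-1 patients.

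- Text route: gap = (a + b) / 210.
- Code route: gap = b / (210 − a).

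With a = 10 and b = 15 (assumed): text 25/210 = 11.9%, so the PPS analysis runs; code 15/200 = 7.5%, so it does not.

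The routes give opposite decisions when a + b > 21 and b ≤ (210 − a)/10. For a = 10 that is every b from 12 to 20; for a = 6 it is b from 16 to 20. Outside those ranges the decision is the same.

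**OTHER16 and FAS-EST**

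Table 5-2 removes only code 1 from FAS-EST, and OTHER16 is code 0. Built from the codes alone, FAS-EST equals the FAS. Built from Section 2.2, it omits patients who stopped treatment because of COVID-19.

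**The case against.** The strongest objection is that the primary estimate may not move. If one missed loading injection counts as an interruption, Protocol Section 12.4.3 already censors that patient's later efficacy data, and the observed Week 12 mean is the same on either route. This stands as a possibility, but the documents do not say whether a single missed injection is an interruption, and FAS counts and denominators differ regardless.

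Second, the trigger example uses invented counts on either side of the 10% line. That is right, and it shows only what could happen. The PPS rows of Table 5-2 also carry a remark about COVID-related deviations; if this adds PPS exclusions, the gap could exceed 10% on both routes. Protocol Section 12.4.4 also lists a PPS repeat without the 10% condition, though among analyses that may be done.

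Third, the FAS definition is not an absolute tie-breaker. INCL03, INCL04, OTHER02 and WITH01 can also remove treated patients from the FAS. In those rows text and code agree, so the intent is plain; for TRT11 it is not. The SAP change log records that severity codes were updated in Section 5.5, so the text could be the stale half. The row's own text, the FAS definition and the parallel treatment deviations (TRT01, TRT02, TRT06, all code 2) nevertheless point to the code as the error.

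Fourth, the deviation criteria are also referred to documents not included here, which may settle the matter in practice. They do not remove the conflict printed in the SAP.

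On OTHER16, the COVID-19 condition could be applied through the FAS-EST definition on top of the codes. That is a workable reading, but it contradicts a row that keeps the patient in all sets.

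**Conclusion.** The concern holds. For patients with a missed loading injection, SAP Section 5.5 gives two answers on membership of the primary analysis set, and the documents do not say which prevails. The text route is better supported, because it matches the FAS definition in both documents.

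The loss of precision is minor: 5.02 to 5.30 at an assumed 10% removed. The size and direction of any shift in the mean cannot be given without TRT11 counts and outcomes, and censoring under Protocol Section 12.4.3 may absorb part or all of it. The most concrete risk is that the PPS analysis is run under one reading and not the other; that rests on assumed counts and on taking 10% as a share of the FAS. The OTHER16 conflict is real but secondary, since FAS-EST is not the primary set. This should be fixed; it does not by itself undermine the design.

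**What to change.** Change the TRT11 severity code from 1 to 2 in Table 5-1, so that the code, the row's text and the FAS definition agree. If exclusion from the FAS was in fact intended, the text entry and the FAS definition must be changed instead, with the reason given. State in Section 5.5 whether text or code governs.

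If the sets have already been built, report which rule was used and the number of TRT11 patients, and show the primary result with and without them.

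Reconcile the OTHER16 row and the FAS-EST row of Table 5-2 with the FAS-EST definition in SAP Section 2.2.

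The cost is one table cell and a short wording correction. No new data are needed; at most, the primary table is run once more.

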### 3 Study design

This is a prospective, single-arm, open-label, multicenter study to evaluate the efficacy and safety of brolicizumab 6 mg in patients with nAMD.

Patients will be required to attend 6 mandatory study visits: Screening/Baseline Visit (Day 1), Week 4, Week 8, Week 12, Week 16 and Week 48 visits. The timing of the interim visits between Week 16 and Week 48 will depend on the patient’s injection regimen, i.e. q12w or q8w.

[figure not shown]
Patients who consent and meet all the inclusion and none of the exclusion criteria will be screened to evaluate eligibility. After confirmation of eligibility, patients will be included and treated with brolicizumab 6 mg.

Approximately 210 adult patients will be screened and included (10% drop-out rate and uninterpretable images at Baseline and Week 12 are expected) in France. The maximum study duration for 1 patient is 48 weeks, including Screening.

There will be 2 periods in this study (see [Figure 3-1](#)):

- Open-label treatment period: from Screening/Baseline (Day 1) to Week 40/Week 44 (depending on assigned regimen)
- Follow-up period: Week 40/Week 44 to Week 48

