### 8.3 Efficacy

The following assessments will be performed to evaluate the effect of brolocizumab on retinal structure, vascular leakage, and visual function:

- Anatomical retinal evaluation of OCT-A and SD-OCT images
- CFP
- FAF
- Vascular evaluation by FA (and optionally by ICG)
- BCVA with ETDRS-like charts at an initial testing distance of 4 meters

All efficacy assessments should be performed **prior** to any administration of study treatment and/or rescue medication.

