### 11.2 Database management and quality control

Novartis (or designated CRO) personnel will review the data entered by investigative staff for completeness and accuracy. Electronic data queries stating the nature of the problem and

requesting clarification will be created for discrepancies and missing values and sent to the investigative site via the EDC system. Designated investigator site staff are required to respond promptly to queries and to make any necessary changes to the data.

Concomitant treatments and prior medications entered into the database will be coded using the World Health Organization (WHO) Drug Reference List, which employs the Anatomical Therapeutic Chemical classification system. Medical history/current medical conditions and AEs will be coded using the Medical Dictionary for Regulatory Activities (MedDRA) terminology.

Ocular images will be handled as described in [Section 8.3.1](#) and [Section 8.3.2](#). The Data management staff will review data received from the CRC. Data Review will be done for data structure and data completeness / accuracy as defined in Vendor Data Transfer Specifications.

The occurrence of relevant PDs will be determined at Week 12 before the interim database lock for the primary analysis and at the conclusion of the study. Once all the necessary actions have been completed and the database has been declared to be complete and accurate, it will be locked. Any changes to the database after that time can only be made after written agreement by Novartis development management.

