1.1 Study design

This is a prospective, single-arm, open-label, multicenter study to evaluate the efficacy and safety of brolucizumab 6 mg in patients with nAMD.

Patients will be required to attend 6 mandatory study visits: Screening/Baseline Visit (Day 1), Week 4, Week 8, Week 12, Week 16 and Week 48 visits. The timing of the interim visits between Week 16 and Week 48 will depend on the patient's injection regimen, i.e. q12w or q8w.

[figure not shown]
Planned number of patients

Approximately 210 adult patients will be screened and included (10% dropout rate and uninterpretable images at Baseline and Week 12 are expected) in France. The maximum study duration for 1 patient is 48 weeks, including Screening.

There will be 2 periods in this study (see Figure 1-1):

- Open-label treatment period: from Screening/Baseline (Day 1) to Week 40/Week 44 (depending on assigned regimen)
- Follow-up period: Week 40/Week 44 to Week 48

Figure 1-1 Study design

^{*} Week 40 or Week 44 according to treatment schedule

Patients will receive 3 initial doses every 4 weeks ((Day 1, Week 4 and Week 8) loading phase), which should be at least 21 days apart, followed by treatment q12w with the possibility of adjusting to treatment q8w based on disease activity.

Disease activity will be assessed based on investigator's judgment of visual acuity and anatomical parameters as provided in the guidance to the investigators, e.g. decrease of visual acuity and/or other signs of the disease (e.g. intraretinal fluid (IRF), subretinal fluid (SRF), sub-retinal pigmented epithelium (sub-RPE) fluid, retinal hemorrhage, central retinal thickness (CRT) increase, etc.). Disease activity will be assessed during the first q12w interval at Week 16. If no disease activity is observed by the investigator in the study eye, disease activity will be assessed every 12 weeks (at Week 20, Week 32 and Week 44). If disease activity is observed by the investigator in the study eye at any of these visits, the study treatment will be adjusted by the investigator to a q8w treatment regimen and will remain on this regimen until Week 40/Week 44. Patients who require study treatment every 4 weeks after the initiation phase will be discontinued from further study treatment at the next visit.

^{**} End of study visit: 4 or 8 weeks after the last IVT, depending on the last IVT date

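### Two PPS exclusion rows (efficacy assessment not done, missed mandatory visit) are not limited to what the Week 12 OCT-A endpoint needs, so valid Baseline–Week 12 pairs can drop out of the robustness set

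*SAP*

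**What the plan says.** SAP Addendum section 5.5, Table 5-1, gives severity code 2 and exclusion from the PPS to two rows: OTHER07, "Missed mandatory visit", and OTHER17, "Efficacy assessment not done". Table 5-2 removes codes 1 and 2 from the PPS. Neither row names a visit, an assessment or an endpoint.

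The mandatory visits are listed in SAP section 1.1 as "6 mandatory study visits: Screening/Baseline Visit (Day 1), Week 4, Week 8, Week 12, Week 16 and Week 48 visits"; Protocol section 3 gives the same list. Protocol section 8.3 counts OCT-A, SD-OCT, colour fundus photography (CFP), autofluorescence (FAF), fluorescein angiography (FA) and BCVA as efficacy assessments, with ICG optional.

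On the endpoint, SAP section 2.5.1 says: "The primary endpoint is the percentage change in CNV lesion area measured by OCT-A from Baseline to Week 12 in the study eye". On when the PPS is used, it says: "The analysis will be performed on the PPS, if there is more than a 10% difference in patients, between the FAS and PPS". Protocol section 12.4.4 lists the PPS repeat as a robustness analysis and also asks for the Week 12 comparison before and after the urgent safety measures in both FAS and PPS. Every secondary efficacy analysis in SAP section 2.6 is assigned to the FAS.

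On timing, Protocol section 11.2 says: "The occurrence of relevant PDs will be determined at Week 12 before the interim database lock for the primary analysis and at" the end of the study. Protocol section 12 bases the primary analysis on data up to and including Week 12.

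**The concern.** A per-protocol set for this endpoint should hold patients treated as planned through loading who have a usable OCT-A at Baseline and Week 12. These two rows also remove patients for events that have no bearing on that pair.

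The lack of limits is not simply the style of the table. TRT06 concerns an injection at Week 12 specifically. TRT11 (a missed injection in the loading phase) is separated from TRT12 (a missed injection generally), and only the former excludes. Meanwhile a patient entered with poor-quality images (EXCL03), with BCVA measured incorrectly (OTHER19) or seen outside the 7-day window (OTHER20) stays in every set. A patient with poor images is therefore kept, while one with a good OCT-A pair and no FAF is dropped.

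At stake is the value of the PPS as a check. Protocol sections 12.1 and 12.4.4 rest confidence in a single-arm descriptive result partly on agreement between FAS and PPS. If PPS membership depends on unrelated tests, or on attendance after the endpoint, neither agreement nor disagreement says much about adherence.

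**Working it through.** **1. The plan's own figures.** Inputs from SAP section 3: SD 35, two-sided 95% CI, target half-width 5.0, 10% loss.

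- Normal approximation: (1.96 × 35 / 5)² = 188.2, rounded up to 189.
- Half-width with Student's t at n = 189: 1.9727 × 35 / √189 = 5.02, shown as 5.0.
- Inflation: 189 / (1 − 0.10) = 210.

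Both stated figures reproduce. They size the FAS analysis on observed data and do not depend on the PPS rows.

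**2. Assessments required and assessments used.** From Protocol Table 8-1, study eye, Day 1 to Week 12:

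| Assessment | Number to Week 12 |
|---|---|
| BCVA, SD-OCT, OCT-A at 4 visits | 4 × 3 = 12 |
| CFP (Day 1, Week 12) | 2 |
| FAF (Day 1, Week 12) | 2 |
| FA (Day 1, Week 12) | 2 |
| Total | 18 |

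The endpoint uses 2 of the 18. The other 16 can each trigger OTHER17, even if nothing after Week 12 is counted.

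**3. Size of the condition for running the PPS analysis.** With 210 in the FAS, a difference above 10% needs a PPS of at most 188: (210 − 188) / 210 = 10.5%, whereas 189 gives exactly 10%.

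**4. Illustration to Week 12.** The documents give no miss rates. Assume a fraction q of visits lacks at least one efficacy assessment, independently across four visits. Fraction excluded = 1 − (1 − q)⁴.

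| q (assumed) | Excluded | Left of 189 | t half-width, SD 35 | Left of 210 | Above 10%? |
|---|---|---|---|---|---|
| 2% | 7.8% | 174 | 5.24 | 194 | No |
| 3% | 11.5% | 167 | 5.35 | 186 | Yes |

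This slightly overstates the valid pairs lost, because some of the misses would be the endpoint scans themselves.

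**5. The same question per assessment.** Counting only the 16 assessments that are not endpoint scans, fraction of valid pairs lost = 1 − (1 − r)¹⁶, for an assumed rate r per assessment:

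| r (assumed) | Pairs lost | Left of 189 | t half-width |
|---|---|---|---|
| 0.2% | 3.2% | 183 | 5.10 |
| 0.5% | 7.7% | 174 | 5.24 |
| 1% | 14.9% | 161 | 5.45 |

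**6. Dates.** Protocol section 11.2 fixes when deviations are determined, and section 12 fixes which data the primary analysis uses. Neither says which deviation dates decide set membership. The lock waits for the last patient's Week 12, so earlier enrolees may by then have passed Week 16 or later visits. How many would be affected depends on the enrolment spread, which the current documents do not give, so no size is attached to this part.

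**The case against.** The strongest reply is that the primary estimate is untouched. It uses observed FAS data, and meeting the 10% condition only adds an analysis that the protocol already lists. That is correct, and it caps the importance of the point.

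A reader might infer that Week 16 and Week 48 absences definitely exclude patients from the Week 12 PPS, and project losses over nine or ten visits (17–26% at the same assumed rates of 2–3%). The documents do not support that. Determining deviations at Week 12, with data limited to Week 12, makes it at least as natural to assign later misses to the end-of-study determination. Ten visits is also the longest path (a switch to q8w at Week 20); otherwise it is nine. What stands is that no cut-off is written.

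Nor does every missed mandatory visit exclude a patient for an unrelated reason. COVID-19 missed visits (OTHER13) carry code 0, although the COVID note in Table 5-2 blurs this. Protocol section 9.1.1 does not require Weeks 16 and 48 after early treatment discontinuation. A missed Week 4 or Week 8 visit bears on the endpoint because loading injections are due then, and a missed Week 12 visit leaves no pair to lose.

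SAP section 2.2 defers the deviation criteria to an edit checks specification that is not available here, so limits may exist there. If so, they belong in Table 5-1, which is presented as the list of excluding deviations.

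A strict, study-wide compliance set is also a legitimate design. But with no Week 48 PPS analysis scheduled in the SAP, requiring complete ancillary imaging or later attendance serves no planned use of the PPS, the related PPS-EST set aside.

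**Conclusion.** The point holds as a defect in the robustness set, not in the primary analysis. On the wording of Table 5-1, OTHER17 removes patients with a valid Baseline–Week 12 OCT-A pair for missing assessments that the endpoint does not use, and this remains true if deviations stop at Week 12. OTHER07 is likewise unrestricted. Whether misses from Week 16 onward count for early enrolees is unresolved, not established.

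The actual loss is unknown. At an assumed 2–3% of visits with a missing assessment, independent across visits, it is about 8–11% of patients to Week 12, with a PPS half-width of about 5.2–5.3 against 5.0. Only the upper end crosses the 10% condition. If misses cluster within patients, fewer patients are affected. The change is worth making before the PPS is derived, because it is cheap and decides who is in the set.

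**What to change.** In SAP Table 5-1, for the PPS of the Week 12 endpoint:

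- Count only deviations dated on or before the patient's Week 12 OCT-A.
- Limit OTHER17 to OCT-A at Baseline or Week 12.
- Limit OTHER07 to Baseline, Week 12, and loading-phase visits missed with the loading injection not given.
- Reconcile TRT11. Its text excludes from the PPS only, but its severity code 1 removes the patient from the FAS under Table 5-2. Until that is settled, missed loading injections cannot safely be left to that row.

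Any limits already in the edit checks specification should be copied into the table. The cost is a table edit and one date condition in the programming, with nothing for sites. The trade-off is a less strict compliance set: on observed data, the OCT-A limits remove few patients beyond those already without a pair, and the PPS then rests mainly on eligibility and treatment deviations.

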#### 12.4.4 Estimand and Sensitivity analyses

In case of significant outliers or deviations from normality assumptions, a non-parametric analysis may be performed.

In order to assess the robustness of the primary endpoint, estimand and sensitivity analyses are planned. These may include, but are not limited to:

- Consistent results from analyses based on the FAS and the PPS increases confidence in the trial results. Difference between FAS and PPS in incidence of intercurrent of event like COVID-19 regardless of whether patients discontinue assigned treatment. Performing comparison on the observed data between FAS vs PPS with the same handling rules for censoring as outlined in [Section 12.4.3](#). for the efficacy endpoints.
- Repeating the primary analysis using the PPS.

**Sensitivity estimand in exposed and non-exposed to the urgent safety measures:** As a sensitivity analysis for the change in CNV lesion area measured by OCT-A at Week 12, the change in CNV lesion area measured by OCT-A at Week 12 will be compared before and after the urgent safety measures were introduced. The analyses will be performed in FAS and PPS.

Further details about the analyses will be given in the SAP. Any major discrepancies in the results across analyses will be investigated as needed.

Age, Baseline lesion type, and time since nAMD diagnosis subgroup analyses will also be performed on the primary endpoint.

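### SAP Tables 5-1 and 5-2 conflict on whether COVID-19 deviations remove patients from the PPS and PPS-EST, and the choice can decide whether the PPS analysis is run

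*SAP*

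**What the plan says.** Three parts of the plan bear on PPS membership.

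- **SAP 5.5, Table 5-1.** Six rows concern COVID-19: "COVID-19 Drug supply change" (TRT09), "COVID-19 Treatment not given" (TRT10), "COVID-19 Missed visit" (OTHER13), "COVID-19 Visit not at site" (OTHER14), "COVID-19 Assessment changed" (OTHER15) and OTHER16, which reads "COVID-19 Discontinuation Included in everything". All six carry severity code 0 and the same instruction to keep the patient in every set.
- **SAP 5.5, Table 5-2.** The right-hand column lists what removes a patient from each set. The PPS entry is "1,2 (All specified PD in Table 5.1 due to COVID", and the PPS-EST entry has the same content. FAS and FAS-EST both show code 1 only.
- **SAP 2.2.** The PPS is the FAS without deviations that have impact, with no COVID-19 rule. The FAS-EST is the FAS without patients who stopped treatment because of COVID-19. The PPS-EST is built on the FAS-EST.

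Two other places use these sets. SAP 2.5.1 repeats the primary analysis on the PPS only if FAS and PPS differ by more than 10% of patients. Protocol 12.4.4 lists, among analyses that may be done, "Difference between FAS and PPS in incidence of intercurrent of event like COVID-19 regardless of whether patients discontinue assigned treatment".

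The SAP contains both Amendment 2.0 and Addendum 1.0. The conflict is in both.

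**The concern.** A programmer cannot follow both tables. If the parenthesis in Table 5-2 adds exclusions, it overrides six explicit instructions in Table 5-1. If it limits codes 1 and 2 to those due to COVID-19, it selects nobody, because no COVID-19 row carries code 1 or 2.

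At stake are the size of the PPS and PPS-EST, possibly whether a PPS sensitivity analysis of the primary endpoint exists at all, and what a FAS-versus-PPS comparison says about COVID-19. If the choice is made after deviations have been reviewed, it is no longer prespecified.

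**Working it through.** **Source of the 210.** The plan gives no figure for set membership, so I use its sample size as the assumed FAS. The normal formula reproduces it: (1.96 × 35 / 5)² = 188.2, rounded up to 189, and 189 / 0.90 = 210. With Student's t the half-width at 189 is 5.02, which rounds to the tabled 5.0.

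**Set logic**

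| Rule programmed | Effect of a COVID-19 row on the PPS | COVID-19 content of FAS versus PPS |
|---|---|---|
| Table 5-1 codes | Removes nobody | None from these rows |
| Table 5-2, parenthesis adds exclusions | Removes every patient with any of the six rows | Present, but mixed with code 2 exclusions and with no visit limit |
| Table 5-2, parenthesis limits codes 1 and 2 | Selects nobody | None |

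The tables also collapse the extra COVID-19 set. FAS-EST excludes code 1 only, as FAS does, and OTHER16 is code 0. As tabulated, FAS-EST equals FAS, against its definition in SAP 2.2.

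**What counts toward the 10% rule.** Code 1 removes a patient from the FAS as well as the PPS, so it adds nothing to the difference. Only code 2 counts, plus COVID-only deviations under the Table 5-2 reading. Let *a* be the share of the FAS with a code 2 deviation and *c* the further share with only a COVID-19 deviation.

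- Table 5-1: difference = *a*; PPS = 210 × (1 − *a*)
- Table 5-2: difference = *a* + *c*; PPS = 210 × (1 − *a* − *c*)

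The tables disagree on running the PPS analysis exactly when *a* ≤ 10% and *a* + *c* > 10%. The rates below are assumptions.

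| *a* | *c* | PPS, Table 5-1 | Run? | PPS, Table 5-2 | Run? |
|---|---|---|---|---|---|
| 5% | 3% | 199.5 | no | 193.2 | no |
| 5% | 10% | 199.5 | no | 178.5 | yes |
| 8% | 3% | 193.2 | no | 186.9 | yes |
| 8% | 10% | 193.2 | no | 172.2 | yes |
| 12% | 10% | 184.8 | yes | 163.8 | yes |

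The first and last rows show no change in the decision. The middle three do.

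**Precision.** I take SD 35, 10% of the PPS lost to dropout or unreadable images, and half-width = t × 35 / √n. At *a* = 8% and *c* = 10%, n is 174 or 155 and the half-width is 5.24 or 5.55. For *a* from 5% to 10% and *c* from 0 to 20%, it is 5.15 to 5.30 under Table 5-1 and 5.15 to 6.03 under Table 5-2.

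**The case against.** The strongest reply is that this is terse wording in a table for a conditional supportive analysis. The primary estimate is on the FAS, whose row has no COVID-19 wording. That is correct, and it limits the weight of the point. It does not settle which patients are in the PPS.

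A reader might infer more than the documents support:

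- **That neither table allows a COVID-19 check.** The natural reading of Table 5-2 does give a FAS-versus-PPS contrast, although a mixed one. The list in protocol 12.4.4 is permissive. SAP section 4, which the change log says gained an analysis for the estimand, shows only its heading in the text available for review. A check described there cannot be ruled out.
- **That a remote visit at, say, Week 40 would drop a valid Baseline–Week 12 pair from the primary PPS.** Table 5-2 sets no visit limit. However, protocol 11.2 determines deviations at Week 12 before the interim lock, and protocol 12 bases the primary analysis on data up to Week 12. The example is therefore doubtful.
- **That every COVID-affected patient stays in the PPS under Table 5-1.** Nothing says the rows are mutually exclusive. A loading injection missed because of COVID-19 could also be logged as TRT11, and a missed Week 12 visit as OTHER07 or OTHER17. The codes show only that the COVID-19 rows themselves remove nobody.
- **That the 10% decision will flip.** This depends on rates that the documents do not give.

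**Conclusion.** The conflict stands. Tables 5-1 and 5-2 cannot both be followed for the PPS and PPS-EST, and the FAS-EST row does not implement its own definition. As little as 3% of patients with only a COVID-19 deviation changes whether the PPS analysis is run if code 2 exclusions stand at 8%. There is no change if code 2 alone exceeds 10% or if the total is 10% or less. These figures assume a FAS of 210, the rates shown, and that the 10% is measured against the FAS.

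The consequence is confined to the sensitivity sets, so this should be corrected but does not threaten the primary FAS estimate. A related mismatch in TRT11 does reach the FAS: its text excludes from the PPS only, but its code is 1, which Table 5-2 also removes from the FAS.

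**What to change.** 1. **Let Table 5-1 govern.** Delete the parenthesis from the PPS and PPS-EST rows of Table 5-2.
2. **Split TRT10 by visit.** Use code 2 when the injection not given was due at Week 4 or Week 8, and code 0 otherwise.
3. **Recode TRT11 from 1 to 2** in the same edit, so that its code matches its text and the COVID-19 and non-COVID rows agree. Copying its present code to TRT10 would remove those patients from the primary analysis set.
4. **Keep code 0** for COVID-19 deviations that do not affect the Baseline–Week 12 data.
5. **Add OTHER16 to the FAS-EST and PPS-EST exclusions**, specified as treatment discontinuation, to match SAP 2.2.
6. **Name the pair of sets that gives the COVID-19 comparison.** After step 5, FAS against FAS-EST differs only by OTHER16. FAS against PPS still mixes COVID-19 with other code 2 deviations.
7. **State whether one event may carry both a COVID-19 and a non-COVID row**, and which code then prevails.

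There is a limit to what recoding can show. The primary analysis uses observed data, so a patient without a Baseline or Week 12 OCT-A contributes to neither set's estimate, and coding that patient 2 adds no contrast. Protocol 12.4.3 also censors efficacy data at the first treatment interruption. If a missed loading injection counts as one, its Week 12 value is absent from both sets. The SAP should say whether it does.

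The cost is table wording and a visit condition in the deviation programming. No new data are needed.
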